7.4 Discontinuation or withdrawal from the study

If a participant is withdrawn from the study, the investigator should always ensure that the end of study page in the case report form (CRF) is completed for withdrawn participants. A participant should be withdrawn from studies, if at any time:

- It is the wish of the participant for any reason
- The investigator judges it necessary due to medical reasons
- Severe non-compliance to the protocol is judged by the investigator

If a participant does not turn up for a scheduled visit, the study personnel will contact him/her by telephone to rearrange the scheduled visit. In any circumstance, every effort should be made to document the participant health status.

7.5 Concomitant medication and care

Along with participation in the studies included patients will continue their usual treatments and scheduled visits and examinations in the outpatient clinic according to usual standard of care and clinical guidelines.

7.6 Outcomes

7.6.1 Primary endpoints

- **Sub study 1:** Difference (monitoring with CGM vs. SMBG) in time spent with glucose value <3.0 mmol/L (level 2 hypoglycaemia) during the last two weeks of each study period
- **Sub study 2:** Long-term glucose variability (up to 48 months) expressed as difference in visit-to-visit HbA1C VIM (Variability Independent of the Mean) between PPDM patients and individuals with type 2 diabetes patients
- **Sub study 3:** Proportions of patients with severe hypoglycaemia during the preceding 12 months. Hypoglycaemic endpoints are defined according to the latest ADA recommendations²¹

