7.3.4 Comparator group for sub study 2 (individuals with type 2 diabetes)

- Individuals with type 2 diabetes enrolled in Diabetesdatabasen are included as comparator group in sub study 2. Diabetesdatabasen is a health registry maintained by the Business Intelligence Unit in the North Denmark Region and collect anonymised data on individuals with diabetes in the North Denmark Region. In agreement with Danish legislation use of anonymised data from Health Registries do not require informed consent from involved individuals.
- Individuals with type 2 diabetes are matched to PPDM patients based on HbA1c levels and other relevant parameters including regimens of glucose lowering therapy

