7.6.2 Secondary endpoints

Sub study 1:

- Short term (20 days) difference in CGM metrics between PPDM patients and individuals with type 2 diabetes
- CGM time in range (glucose value >3.9 mmol/L and ≤10 mmol/L)
- CGM time below range (glucose value ≤3.9 mmol/L)
- CGM time above range (glucose value >10 mmol/L)
- CGM metrics of glucose variability (SD (Standard deviation) and CV (Coefficient of Variance) of mean glucose, mean amplitude of glycaemic excursions [MAGE] and continuous overall net glycaemic action [CONGA])

Sub study 2:

- Difference in HbA1C CV between PPDM and type 2 diabetes patients during up to 48 months follow-up
- Difference in HbA1C average real variability between PPDM and type 2 diabetes patients during up to 48 months follow-up
- Difference in HbA1C level trajectories between PPDM and type 2 diabetes patients during up to 48 months follow-up

Sub study 3:

- Risk factors for hypoglycaemia including demographics and routine clinical and biochemical parameters
- Awareness of hypoglycaemia based on the Clarke hypoglycaemia awareness survey
- Proportions of patients with ketoacidosis during the preceding 12 months

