Arginine stimulation test	X						
Questionnaires	X			X			X
Registration of adverse events				X			X
Unloading CGM transmitter		X	X*	X	X	X*	X

*Unloading the CGM transmitter applies only when the participants are being monitored using unmasked CGM

7.7.2 Sub study 2

Sub study 2 is based on data from Diabetesdatabasen in the North Denmark Region and therefore no study-related visits or procedures pertain to patients included in sub study 2. The database is maintained and managed by the Business Intelligence unit in the North Danish Region.

7.7.3 Sub study 3

Patients with PPDM will primarily be included from the outpatient clinics of participating centres as outlined above. Following written informed consent, patients are asked to fulfil the relevant questionaries as described below. The required time to fulfil the questionaries is approximately 30 minutes, making total time required for participation in the study a maximum of 60 minutes. Patients can either choose to fill in the questionaries in the outpatient clinic or bring the questionnaires to their home and return them via postal service (stamped envelopes are provided for free) or alternatively use digital questionnaires linked to the individual subject's CRF in REDCap (see section 8.2.1).

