7.8 Sample size considerations

- **Sub study 1:** The sample size calculation is based on the primary endpoint described for sub study 1 (time in level 2 hypoglycaemia). A sample size of 24 patients is determined to have at least 80% power to detect a reduction in the percentage of time spent with a glucose value <3.0 mmol/l (level 2 hypoglycaemia), assuming a relative treatment reduction of 50% from a percentage of time spent with glucose value <3.0 mmol/l of 3%, standard error of 2.5%, and type I error rate (2 sided) of 5%. To account for approximately 25% dropouts, the final sample size is set to 30 patients. As there are currently no adequate data on CGM in patients with pancreatogenic diabetes to inform sample size calculations, assumptions are based on findings in older adults with long-standing type 1 diabetes who have an increased risk of hypoglycaemia⁷.
- **Sub study 2:** This is a retrospective cohort study based on data already collected in Diabetesdatabasen and the sample size will therefore be dictated by the number of individuals in the

database. Previous population-based studies from our group have shown that the proportion of patients with PPDM among patients clinically diagnosed type 1 or type 2 diabetes is approximately 1.5%^{4,22}. In Diabetesdatabasen there are currently >5000 unique adult individuals registered, and thus we expect to identify at least 75 PPDM cases which should provide sufficient statistical power to the planned analyses according to a previous study from our group²².

- **Sub study 3:** This is a cross-sectional survey. No previous studies have evaluated the prevalence of self-reported severe hypoglycaemia and related risk factors in patients with PPDM. However, according to recent population-based registry data from our group, patients with PPDM have a risk of hospitalization for hypoglycaemia comparable to that observed for individuals with type 1 diabetes (*unpublished data*). In type 1 diabetes, the yearly prevalence of self-reported severe hypoglycaemia range between 10–53%²³. Thus, we consider a sample size of 200 patients will provide sufficient power to obtain prevalence estimates with reasonable precision and allow for multivariate modelling of putative risk factors associated with severe hypoglycaemia.

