8.3 Plan for statistical analyses

8.3.1 Statistical methods

- **Sub study 1:** CGM metrics collected in periods with monitoring using CGM vs. SMBG are compared using multiple linear regression models. Further, regression models are fitted to investigate associations between baseline characteristics and measures of glucose variability.
- **Sub study 2:** HbA1c variability metrics are compared between PPDM and type 2 diabetes patients using multiple linear regression models. Hb1Ac level trajectories are visually characterized and latent class analysis is used to define distinct patient clusters.
- **Sub study 3:** Prevalence estimates of hypoglycaemia are reported as point prevalence estimates with 95% confidence intervals. Logistic and Poisson regression models are fitted to investigate associations between patient characteristics and hypoglycaemia risk.

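### Sub study 2 compares HbA1c variability over windows of any length up to 48 months, without a common window or testing pattern for the matched groups, so unequal follow-up or testing could pass for, or mask, a difference in variability

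*Protocol*

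**What the plan says.** Protocol section 7.6.1 defines the primary endpoint of sub study 2 as "Long-term glucose variability (up to 48 months) expressed as difference in visit-to-visit HbA1C VIM", contrasted between PPDM and type 2 diabetes patients. Section 7.6.2 applies the same open window to two further metrics: "Difference in HbA1C CV between PPDM and type 2 diabetes patients during up to 48 months follow-up" and "Difference in HbA1C average real variability between PPDM and type 2 diabetes patients during up to 48 months follow-up". In each case 48 months is an upper limit. No minimum follow-up and no common window for the two groups is given.

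The HbA1c values come from a regional register. Section 7.7.2 notes that "no study-related visits or procedures pertain to patients included in sub study 2", so the protocol does not schedule the tests. Their number and timing follow routine care.

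Two passages could make the groups comparable. Section 7.3.4 says comparators are "matched to PPDM patients based on HbA1c levels and other relevant parameters including regimens of glucose lowering therapy". That list is open-ended, but it names neither length of follow-up nor number or spacing of tests. Section 8.3.1 says "HbA1c variability metrics are compared between PPDM and type 2 diabetes patients using multiple linear regression models", without naming covariates.

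**The concern.** VIM and CV are both built on each patient's own standard deviation of HbA1c. If HbA1c wanders slowly, a longer window captures more of the wandering and the standard deviation is larger, although the patient is no more unstable. Average real variability is the mean absolute change between consecutive tests. For a slowly moving quantity it shrinks when tests are close together. None of the three is therefore a property of the patient alone. Each also reflects how long and how often the patient was observed.

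If PPDM and type 2 patients differ in these respects, the comparison mixes observation with biology. The direction is not fixed. Shorter follow-up in the PPDM group would pull its VIM down and could hide a true excess. Shorter follow-up among comparators would create an apparent one. The primary conclusion of sub study 2 is at stake.

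**Working it through.** **Stated figure.** Section 7.8 says "there are currently >5000 unique adult individuals registered" and puts the PPDM share at about 1.5%. 5000 × 0.015 = 75, which matches the expected minimum of 75 cases. No effect size, SD or power is given for sub study 2, so nothing further can be reproduced.

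**Step 1: number of tests, independent readings.** For independent normal readings with the n−1 divisor, the expected SD as a share of the true SD is c4(n) = √(2/(n−1)) · Γ(n/2) / Γ((n−1)/2).

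| Tests | 2 | 3 | 4 | 5 | 8 | 9 | 16 |
|---|---|---|---|---|---|---|---|
| c4 | 0.798 | 0.886 | 0.921 | 0.940 | 0.965 | 0.969 | 0.983 |

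The loss is material at two or three tests. From 5 to 9 tests the change is 0.969/0.940 − 1 = 3%.

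**Step 2: simulation set-up.** None of these inputs is in the protocol; all are assumptions.

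- Mean HbA1c 60 mmol/mol, between-patient SD 8, within-patient SD 7.
- Equally spaced tests.
- VIM = SD × (60 / patient mean)^1.5.
- Autocorrelated process: exponential correlation with a 9-month scale, plus measurement SD 2.
- Drift process: the same, plus a patient slope with SD 0.15 mmol/mol per month.

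Both groups follow the same process, so any group difference is spurious.

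**Step 3: effect of the window, five tests per patient.**

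| Mean VIM | 12 months | 24 months | 48 months | Rise, 12 to 48 |
|---|---|---|---|---|
| Autocorrelated | 5.06 | 5.97 | 6.69 | 6.69/5.06 = 1.32 |
| With drift | 5.08 | 6.14 | 7.26 | 7.26/5.08 = 1.43 |

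With independent readings the window has no effect.

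**Step 4: effect of test count, window fixed at 48 months, autocorrelated.**

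| Tests | 3 | 5 | 9 | 17 |
|---|---|---|---|---|
| Mean VIM | 6.59 | 6.69 | 6.57 | 6.46 |
| Mean average real variability | 7.91 | 7.13 | 5.94 | 4.77 |

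VIM is nearly flat. Average real variability falls by 1 − 4.77/7.91 = 40%. With independent readings it is flat, at about 7.9.

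**Step 5: false positives for VIM.** 75 against 75 patients, unadjusted Welch t-test, two-sided 5%, 10,000 simulated comparisons per row. The gap is the first group relative to the second.

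| Months/tests, group A vs B | Autocorrelated: gap, rejection | With drift: gap, rejection |
|---|---|---|
| 48/9 vs 48/9 | 0%, 5% | 0%, 5% |
| 36/5 vs 48/5 | −4%, 8% | −6%, 14% |
| 36/7 vs 48/9 (six-monthly) | −3%, 8% | −5%, 13% |
| 36/9 vs 48/9 | −4%, 11% | −7%, 18% |
| 24/5 vs 48/5 | −11%, 31% | −15%, 54% |
| 24/5 vs 48/9 (six-monthly) | −9%, 28% | −12%, 45% |
| 24/9 vs 48/9 | −12%, 49% | −15%, 69% |
| 48/9 vs 48/5 | −2%, 5–6% | −3%, 7% |

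With 300 comparators, the 24/5 vs 48/5 row rises to 49% and 78%. CV behaves like VIM, with somewhat higher rejection (about 38% and 65% in the 24/5 vs 48/5 row at 75 against 75).

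Average real variability behaves differently. In the last row (9 vs 5 tests, same window) it shows a spurious gap of −17% to −18% with 86–92% rejection. In the six-monthly rows, where spacing is equal, it stays at about 5% despite the unequal windows.

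**The case against.** The strongest reply is that much of this is statistical analysis plan detail. Section 8.3.1 names a model class and leaves covariates open. Section 7.3.4 allows matching on further relevant parameters, which could include follow-up and testing. A maximum look-back is normal in a retrospective register study. This stands for the minimum number of tests, the SD divisor and the VIM exponent, which can be left to that plan. It does not dispose of the window. The window is part of the endpoint definition, and sections 7.6.1 and 7.6.2 state it in a form that allows unequal observation. The explicit deferral in section 8.3.3 concerns missing data only.

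A second reply is that no imbalance is shown. Both groups' data come from the same register, and the protocol reports neither test counts nor follow-up by group. This stands. Section 7.2 says PPDM patients are mainly identified through a specialist pancreas clinic, which makes different testing plausible but does not establish it. The contrasts above also put every patient in one group on the shorter window; a partial imbalance would do less.

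Two stronger readings might be inferred and are not supported. One is that all the metrics grow with both window and number of tests. Steps 3 and 4 contradict it: VIM and CV need autocorrelation or drift to grow with the window, VIM hardly moves between 5 and 9 tests, and average real variability falls with denser testing. The other is that matching is confined to HbA1c and treatment, or that regression cannot help. The matching list is open, and the planned regression could carry number and spacing of tests as covariates.

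**Conclusion.** The point holds as a conditional risk. Followed as written, the plan can compare VIM and CV over unequal windows, and average real variability over unequal test spacing, and nothing it names prevents this. For the primary endpoint, window length is the main exposure; test count is minor unless tests are very few.

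With no true difference, 75 against 75 patients and five tests each, the false-positive rate for VIM is about 8–14% for 36 against 48 months and 31–54% for 24 against 48. It reaches about 70% for 24 against 48 months with nine tests each and drift. With equal windows and test counts it is about 5%. These sizes depend on the assumed mean, SDs, correlation scale, drift, exponent and equal group sizes, and on a uniform difference in follow-up between groups. If readings were independent, unequal windows alone would do no harm. Severity is minor to moderate.

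**What to change.** In sections 7.6.1, 7.3.4 and 8.3.1, and before any group comparison is seen:

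1. Compute VIM, CV and average real variability over the same window for all members of a matched set, or match on length of follow-up.
2. Match on, or adjust for, the number of HbA1c tests and their mean spacing. Adjustment works only where the two groups overlap on these, so report their distributions by group.
3. Keep the analysis using all values up to 48 months as a sensitivity analysis.

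The minimum number of tests and the VIM exponent can stay with the statistical analysis plan.

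The data are already collected, so the work is programming. The price is that some later HbA1c values go unused in the primary analysis, with a small loss of precision. If sets are cut to their shortest member, the loss grows with the number of comparators per case, which the protocol does not state. Matching on follow-up length avoids most of that, but narrows the pool of comparators.

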7.6.2 Secondary endpoints

Sub study 1:

- Short term (20 days) difference in CGM metrics between PPDM patients and individuals with type 2 diabetes
- CGM time in range (glucose value >3.9 mmol/L and ≤10 mmol/L)
- CGM time below range (glucose value ≤3.9 mmol/L)
- CGM time above range (glucose value >10 mmol/L)
- CGM metrics of glucose variability (SD (Standard deviation) and CV (Coefficient of Variance) of mean glucose, mean amplitude of glycaemic excursions [MAGE] and continuous overall net glycaemic action [CONGA])

Sub study 2:

- Difference in HbA1C CV between PPDM and type 2 diabetes patients during up to 48 months follow-up
- Difference in HbA1C average real variability between PPDM and type 2 diabetes patients during up to 48 months follow-up
- Difference in HbA1C level trajectories between PPDM and type 2 diabetes patients during up to 48 months follow-up

Sub study 3:

- Risk factors for hypoglycaemia including demographics and routine clinical and biochemical parameters
- Awareness of hypoglycaemia based on the Clarke hypoglycaemia awareness survey
- Proportions of patients with ketoacidosis during the preceding 12 months

7.6.3 Explorative endpoints

In sub study 1 an arginine test is employed to study pancreatic endocrine secretory capacity (insulin and glucagon). In addition, various baseline characteristics of PPDM patients including pancreatic and intestinal hormone profiles are associated with CGM metrics to explore putative mediators of short-term glucose variability.

7.7 Participant timelines

7.7.1 Sub study 1

Patients with PPDM will primarily be included from the outpatient clinic at Centre for Pancreatic Diseases, Aalborg University Hospital as outlined below (7.9). Following written informed consent,

participants are randomized to monitoring with CGM followed by SMBG for 50 days or *vice versa*. Each study period is initiated by 20 days masked CGM (baseline) and patients using SMBG will also wear a masked CGM during the last 20 days of the SMBG period to allow comparison of CGM based endpoints between the two study periods. A timeline of study activities is illustrated in figure 2.

[figure not shown]

Figure 2. Timeline of sub study 1. CGM; Continuous glucose monitoring, SMBG; Self-monitoring of blood glucose.

Participants will undergo a total of 7 study visits, as illustrated in figure 2. The duration of the baseline visit (visit 1) is approximately 120 minutes, and the subsequent visits 15-30 minutes, making the total time required for participation in the study a maximum of 300 minutes. At the baseline visit, height and weight are registered, and body mass index is calculated. Pancreatic function (exocrine and endocrine) will be evaluated based on review of patients' medical records and supplemented by routine biochemical tests including autoantibodies and HbA1c. Also, blood is drawn for biobanking and assessment of basal intestinal and pancreatic hormone levels. An arginine stimulation test is done to assess endocrine pancreatic secretory capacity. Patients are instructed in use of an insulin and food diary and fill in questionnaires. Finally, the CGM sensor is mounted and activated. Every 10 days the CGM glucose sensor is changed by the participant at home based on instructions from study staff (or alternatively they can choose to have the censor changed in the diabetes outpatient clinic). After 20 ± 2 days (visit 2), participants meet to either unmask or remove the CGM. Then, on day 50 ± 2 (visit 3), the participant with unmasked CGM returns to unload the CGM transmitter, while the participants randomized to SMBG come in and the CGM is again mounted and masked. The study periods end at day 70 ± 2 , where participants meet for a follow-up visit (visit 4), where the CGM transmitter is unloaded. The food and insulin diary is collected and reviewed together with the patient to ensure accurate registrations of insulin administration and food intake. Patients fill in questionnaires and adverse events in relation to CGM monitoring or other study activities are registered. Since crossover will occur immediately at the end of the first study period, visit 4 in period 1 and visit 1 in period 2 are merged. Also, baseline data is only collected at the very first visit. In **Table 1** an overview of the various study activities in sub study 1 is reported.

Table 1: Participant timeline and study activities for sub study 1

	Study period 1			Study period 2			
	Baseline Visit 1 Day 0	Visit 2 Day 20	Visit 3 Day 50	Visit 4/1 Day 70/0	Visit 2 Day 20	Visit 3 Day 50	Visit 4 Day 70
Anthropometrics	X						
Biochemistry							
- Faecal elastase	X						
- HbA1c	X			X			
- Routine biochemistry	X						
- Blood for biobanking	X						
- Autoantibodies	X						
- C-peptide	X						
Arginine stimulation test	X						
Questionnaires	X			X			X
Registration of adverse events				X			X
Unloading CGM transmitter		X	X*	X	X	X*	X

*Unloading the CGM transmitter applies only when the participants are being monitored using unmasked CGM

7.7.2 Sub study 2

Sub study 2 is based on data from Diabetesdatabasen in the North Denmark Region and therefore no study-related visits or procedures pertain to patients included in sub study 2. The database is maintained and managed by the Business Intelligence unit in the North Danish Region.

7.7.3 Sub study 3

Patients with PPDM will primarily be included from the outpatient clinics of participating centres as outlined above. Following written informed consent, patients are asked to fulfil the relevant questionaries as described below. The required time to fulfil the questionaries is approximately 30 minutes, making total time required for participation in the study a maximum of 60 minutes. Patients can either choose to fill in the questionaries in the outpatient clinic or bring the questionnaires to their home and return them via postal service (stamped envelopes are provided for free) or alternatively use digital questionnaires linked to the individual subject's CRF in REDCap (see section 8.2.1).

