9.1 Risk and benefits

The risks and potential side effects associated with participation in the study are considered to be limited. Biochemical tests including blood samples and fecal-elastase1 as well as CGM bear little risk for the patients and furthermore are all part of the standard evaluation/management of the disease. Potential side effects include the inconvenience and slight discomfort associated with blood sampling. Furthermore, use of the CGM can rarely cause local skin irritation and increased risk of infection. The potential benefit, on the other hand, is significant, as the proposed studies are expected to provide insight into modifiable risk factors for hypoglycaemia and to identify targets for improved glycaemic control in PPDM. As many of parameters under investigation are available through routine clinical management, it will be straightforward to implement findings into clinical practice. It is envisioned that information from the proposed studies can be used to identify patients at excess risk of hypoglycaemia and thus to optimize clinical management including intensified outpatient monitoring strategies. Accordingly, most patients with PPDM are currently treated by general practitioners that may have limited knowledge of the special considerations for management of PPDM. Identification of PPDM patients with high risk of complications would facilitate a rational triage of patients to specialized outpatient clinics with special interest in PPDM management.

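### Adverse events in sub study 1 are scheduled for registration only at the two period-end visits (days 70 and 140) of seven attended visits; marking the other five is a cheap improvement

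*Protocol*

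**What the plan says.** Section 7.7.1 sets the visit count: "Participants will undergo a total of 7 study visits, as illustrated in figure 2". In Table 1 the seven columns are days 0, 20, 50 and 70/0 of period 1 (the last merged with the start of period 2), then days 20, 50 and 70 of period 2.

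The row "Registration of adverse events X X" has its two marks in columns 4 and 7. The text places registration at the same point: "The study periods end at day 70 ± 2 , where participants meet for a follow-up visit (visit 4)", and in the account of that visit, "Patients fill in questionnaires and adverse events in relation to CGM monitoring or other study activities are registered".

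The arginine test belongs to the first visit. The text says "An arginine stimulation test is done to assess endocrine pancreatic secretory capacity", and the Table 1 row "Arginine stimulation test X" has its single mark in the day 0 column. The day 20 visit is attended in person and divides masked baseline from the randomised phase: "After 20 ± 2 days (visit 2), participants meet to either unmask or remove the CGM". Section 9.1 names the device risks: "use of the CGM can rarely cause local skin irritation and increased risk of infection".

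**The concern.** Section 7.7.1 sets out to register events linked to CGM or to other study activities. The two main sources of such events are the arginine infusion on day 0 and a series of sensors changed every 10 days, mostly at home. A schedule that asks only at the end of each 70-day period relies on patients remembering mild and short-lived events, such as local skin reactions, over several weeks.

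The schedule also passes over the day 20 visit, the natural place to close the masked baseline. Each registration then covers a 20-day baseline that is the same in both arms, plus 50 days under CGM or SMBG. At stake are the completeness of the safety data and the ease of assigning events to a study phase. Efficacy is not involved.

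**Working it through.** **Inputs.** Visit days and marks come from Table 1. The ±2 day window, the 10-day sensor change and the wear pattern come from section 7.7.1.

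**Step 1: reproduce the schedule.** Adding 70 to the period 2 days gives cumulative visit days 0, 20, 50, 70, 90, 120 and 140. The adverse-event marks in columns 4 and 7 fall on days 70 and 140, so 2 of 7 visits. As a check on column alignment, the questionnaire row falls on days 0, 70 and 140, and the transmitter row on days 20, 50, 70, 90, 120 and 140. Both fit the text, so the two marks are not an artefact of a broken table.

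**Step 2: delay from event to scheduled registration.**

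| Event | Occurs (day of period) | Registered (day of period) | Delay |
|---|---|---|---|
| Arginine infusion | 0 (period 1 only) | 70 | 70 − 0 = 70 days (68 to 72 with the window) |
| Masked baseline | 0 to 20 | 70 | 70 − 20 = 50 to 70 − 0 = 70 days |
| Randomised phase | 20 to 70 | 70 | 70 − 70 = 0 to 70 − 20 = 50 days |

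The last two rows apply equally to period 2, where registration falls on cumulative day 140.

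**Step 3: sensor exposure covered by the two registrations.** This assumes the wear pattern of section 7.7.1, with the sensor worn throughout the CGM period.

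- CGM period: 70 days / 10 = 7 sensors.
- SMBG period: (20 + 20) days / 10 = 4 sensors.
- Total: 70 + 40 = 110 wear days and 7 + 4 = 11 sensors.

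**Step 4: mix of phases.** Each registration spans 20 baseline days plus 50 randomised days. Over the study, 2 × 20 = 40 of 140 days are masked baseline.

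**Step 5: the schedule if every attended visit were used.** The intervals would be 20, 30, 20, 20, 30 and 20 days, so the longest would fall from 70 to 30 days. An entry after the infusion on day 0 would remove the 70-day gap for that procedure.

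**Step 6: is the gap closed elsewhere?** The telephone line in section 8.1.1 is for technical problems. The rule in section 8.2 that data are recorded gradually from inclusion is general. Neither sets an adverse-event step. The protocol does not say whether onset dates are recorded.

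**The case against.** The strongest reply is that nothing here is misstated: table and text agree, and no primary, secondary or exploratory endpoint in section 7.6 depends on adverse events. That stands, and it limits the point to a minor one.

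A reader might also draw four stronger conclusions, none of which the document supports.

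- **That baseline and randomised-phase events cannot be separated.** Attribution depends on the onset date, not on how often patients are asked. An event registered on day 70 with an onset date can be placed before or after day 20. The protocol is silent on onset dates, so separation is only not ensured.
- **That the tolerability of CGM and SMBG cannot be compared.** The day 70 registration itself divides period 1 from period 2. The masked baseline has the same length in both periods, so pooling it dilutes the contrast without removing it. Masked sensor wear in the SMBG period is needed for the primary endpoint, and more registrations would not change it.
- **That arginine reactions rest on 70-day recall.** Section 8.1.5 has blood drawn up to 30 minutes after the infusion, within a visit of about 120 minutes, so staff are present for an acute reaction. What is missing is a written step to register it.
- **That a patient who leaves before day 70 goes undocumented.** Section 7.4 requires the end-of-study page of the case report form to be completed and asks for every effort to document health status. It does not name adverse events, so it covers this gap only in part. Section 7.8 allows for 30 − 24 = 6 dropouts; how many would fall before day 70 is not stated.

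Finally, section 9.1 calls the device reactions rare, and the document gives no rate of under-reporting. The loss is plausible but cannot be quantified.

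**Conclusion.** The schedule is thinner than the visit plan allows. Registration is fixed at two of seven attended visits, the first about 70 days after the only infusion, with masked-baseline events registered 50 to 70 days after they occur. Mild infusion and sensor-site events may be under-captured, and assignment to phase within a period depends on onset dates that the protocol does not mention.

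This rests on reading Table 1 as the complete schedule, which the text supports, and on sensor wear as described in section 7.7.1. It also assumes that longer recall loses mild events, which the document's own data cannot test. The CGM-based primary endpoint and the listed secondary endpoints are untouched. The point is a cheap improvement of minor severity, and neither an error nor a contradiction.

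**What to change.** In Table 1 and the text of section 7.7.1, mark registration of adverse events at every attended visit: at visit 1 after the arginine test, then at visits 2, 3 and 4 of each period. Require an onset date for each event, so that it can be assigned to masked baseline, CGM phase or SMBG phase and reported that way.

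The cost is a few minutes at five visits that already take place, a change to one table row and the matching text, and repeats of the case report form. No visit is added, and the sample size does not change.
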